### 9.3.2 Laboratory Evaluations

Samples for laboratory assays will be sent to a central laboratory for analysis, except for the baseline urine pregnancy test which will be analyzed locally. Detailed instructions for the collection, processing, and shipment of laboratory samples will be provided by the sponsor and the central laboratory. The investigator is responsible for reviewing laboratory results for clinical significance.

The following laboratory evaluations will be conducted during the study:

- Serum and urine pregnancy tests: Female subjects who are of childbearing potential (ie, are not surgically sterile or postmenopausal) will participate in serum pregnancy tests (to be analyzed by the central lab) and urine pregnancy tests (to be analyzed by the local lab). The screening and baseline pregnancy test results must be available and must be negative for a subject to initiate or continue study drug. Additional pregnancy tests may be conducted during the study to establish the absence of pregnancy based on the investigator's clinical judgment or as required by local regulations.
- Coagulation tests: Blood sample will be collected to assess the prothrombin time (PT), partial thromboplastin time (PTT), and international normalized ratio (INR).

- Folate and vitamin B12: Blood sample will be collected to assess folate and vitamin B12 levels.
- Urine albumin-to-creatinine ratio (uACR): A random urine spot sample will be collected to provide the uACR. Subjects should refrain from heavy exercise 24 hours before the test.
- CBC: Including Hb, hematocrit, RBC count, mean corpuscular volume, mean corpuscular Hb, mean corpuscular Hb concentration, red cell distribution width, white blood cell count with differential (neutrophils, bands, lymphocytes, monocytes, eosinophils, and basophils), platelets, and automated reticulocyte count (both absolute and percent).
- Chemistry and eGFR: Including sodium, potassium, bicarbonate, chloride, calcium, phosphorus, glucose, creatinine, blood urea nitrogen, creatine phosphokinase, uric acid, albumin, total protein, total bilirubin, alkaline phosphatase, ALT (SGPT), AST (SGOT), lactate dehydrogenase (LDH), and total cholesterol. eGFR will be calculated from serum creatinine as described in [Appendix B](#). Glucose will be measured using plasma samples and the other chemistry parameters will be measured using serum samples.
- Iron indices: Blood samples will be collected to assess serum iron, TIBC, TSAT, and ferritin.
- Hepcidin: Blood samples will be collected to assess hepcidin.
- C-reactive protein: Blood sample will be collected to assess C-reactive protein.
- VEGF: Blood sample will be collected to assess VEGF levels.
- PK analysis: Week 4 pre-dose sample will be analyzed for vadadustat and its metabolites. Study drug dose on this day should be held until after the pre-dose PK sample has been obtained. After the labs are drawn, the subject should take their scheduled dose of study drug.

Blood samples will be collected in tubes with K2EDTA anticoagulant, plasma prepared, and frozen within 1 hour of blood collection. Analysis of samples for vadadustat and metabolite concentration determinations will be performed by a sponsor-designated contract research organization (CRO) using a validated Liquid Chromatography-Mass Spectrometry and Liquid Chromatography-Tandem Mass Spectrometry (LC-MS/MS) method. Detailed instructions for collection, processing, storage, and shipment of the samples for PK and metabolite analyses will be provided by the sponsor or a designated laboratory.

## 9.4 Schedule of Activities

The Schedule of Events in [Appendix A](#) shows the timing of planned study procedures. Every effort should be made to adhere to this procedure schedule and all assessments should be completed at each study visit.

### 9.4.1 Screening Visit

The screening visit must be performed within 28 days prior to dosing and there must be a minimum of 4 days between the last qualifying repeat measurement and the baseline visit (Day 1).

After obtaining informed consent and receiving a unique subject identification number, subjects will undergo screening activities. The investigator will maintain a log of subjects and indicate who was enrolled or excluded and the reason for exclusion (see [Section 9.2.2](#)).

At the screening visit, the following activities/procedures will be performed:

- Signing of informed consent
- Review of study inclusion and exclusion criteria
- Demographics, medical history, and physical examination
- Weight assessment
- Vital signs (heart rate and blood pressure should be assessed in a seated position after 5 minutes of rest and prior to blood draws)
- Prior and current medication review
- Laboratory procedures:
  - Serum pregnancy test for females of childbearing potential (eligible subjects will be advised to use an adequate contraceptive method). The serum pregnancy test will be analyzed by the central lab. The screening results must be available and must be negative before the subject takes the first dose of study drug.
  - Folate and vitamin B12 levels
  - CBC
  - Chemistry and eGFR
  - Iron indices

#### **9.4.2 Baseline Visit (Day 1)**

There must be a minimum of 4 days between the screening and baseline visits.

At the baseline visit, the following activities/procedures will be performed:

- Review of study inclusion and exclusion criteria
- Vital signs (heart rate and blood pressure should be assessed in a seated position after 5 minutes of rest and prior to blood draws)
- 12-lead ECG (prior to blood draws when possible and obtained after the subject has been resting supine comfortably for approximately 10 minutes)
- AE review
- Recording of any concomitant medication use since screening visit
- Laboratory procedures:
  - Urine pregnancy test for females of childbearing potential (eligible subjects will be advised to use an adequate contraceptive method). The urine sample will be analyzed by the local lab. The baseline results must be available and must be negative before the subject takes the first dose of study drug.
  - Coagulation tests (including prothrombin time, partial thromboplastin time, and international normalized ratio)
  - Urine albumin-to-creatinine ratio (uACR through random urine spot sample)
  - CBC
  - Chemistry and eGFR
  - Iron indices
  - Hepcidin
  - C-reactive protein

- VEGF
- Dispense one bottle of study drug
- Review dosing instructions

#### 9.4.3 Week 2 Visit

At the Week 2 visit, the following activities/procedures will be performed:

- Vital signs (heart rate and blood pressure should be assessed in a seated position after 5 minutes of rest and prior to blood draws)
- AE review
- Rescue therapy (ESA rescue and RBC transfusion) review
- Concomitant medication review
- Laboratory procedures:
  - CBC
  - Chemistry and eGFR
  - Iron indices
- Dispense study drug (as necessary)
- Subjects should be questioned regarding dosing compliance
- Review dosing instructions and remind subjects that they may be contacted by telephone to discuss dose reduction or interruption if central lab Hb result demonstrates excess Hb response
- Remind/instruct subjects to hold their dose of study medication on the day of the Week 4 visit until after the pre-dose PK blood sample has been collected
- If central lab Hb result obtained from this visit demonstrates excess Hb response, contact subject for dose reduction ([Section 8.2.4](#))

#### 9.4.4 Week 4 Visit

When possible, this visit should be scheduled in the morning due to the pre-dose PK evaluation. The morning dose of study medication should be held until after the pre-dose PK sample is drawn.

At the Week 4 visit, the following activities/procedures will be performed:

- Vital signs (heart rate and blood pressure should be assessed in a seated position after 5 minutes of rest and prior to blood draws)
- AE review
- Rescue therapy (ESA rescue and RBC transfusion) review
- Concomitant medication review
- Laboratory procedures:
  - CBC
  - Chemistry and eGFR
  - Iron indices
  - Pre-dose PK sample (record date and time of the last dose of the study drug that was taken prior to the pre-dose PK sample)
- Dispense study drug (as necessary)
- Subjects should be questioned regarding dosing compliance

- Review dosing instructions and remind subjects that they may be contacted by telephone to discuss dose reduction or interruption if central lab Hb result demonstrates excess Hb response
- If central lab Hb result obtained from this visit demonstrates excess Hb response, contact subject for dose reduction ([Section 8.2.4](#))

#### 9.4.5 Week 6 Visit

At the Week 6 visit, the following activities/procedures will be performed:

- Vital signs (heart rate and blood pressure should be assessed in a seated position after 5 minutes of rest and prior to blood draws)
- AE review
- Rescue therapy (ESA rescue and RBC transfusion) review
- Concomitant medication review
- Laboratory procedures:
  - CBC
  - Chemistry and eGFR
  - Iron indices
  - Hepcidin
  - C-reactive protein
  - VEGF
- Collect study bottle and all remaining study drug tablets remaining from the primary efficacy period
- Dispense one bottle of vadadustat
- Subjects should be questioned regarding dosing compliance
- Review dosing instructions and remind subjects that they may be contacted by telephone to discuss dose adjustment or interruption depending on central lab Hb result
- If central lab Hb result obtained from this visit supports dose adjustment based on dose adjustment guidelines, contact subject for dose adjustment ([Section 8.2.5](#))

#### 9.4.6 Week 8, 10, 12, 14 Visits

At these visits, the following activities/procedures will be performed:

- Vital signs (heart rate and blood pressure should be assessed in a seated position after 5 minutes of rest and prior to blood draws)
- AE review
- Rescue therapy (ESA rescue and RBC transfusion) review
- Concomitant medication review
- Laboratory procedures:
  - CBC
  - Chemistry and eGFR
  - Iron indices (Week 8 and Week 12 visits only)
- Dispense vadadustat (as necessary)
- Subjects should be questioned regarding dosing compliance
- Review dosing instructions and remind subjects that they may be contacted by telephone to discuss dose adjustment depending on central lab Hb result

- If central lab Hb result obtained from this visit supports dose adjustment based on dose adjustment guidelines, contact subject for dose adjustment ([Section 8.2.5](#))

#### **9.4.7 Week 16 Visit (end-of-treatment visit for subjects who complete the dose adjustment and maintenance period or for subjects who withdraw prematurely from the study prior to Week 16)**

All subjects should complete the Week 16 assessments.

Subjects who withdraw prematurely from the study prior to the Week 16 visit, should undergo the clinical and laboratory assessments specified below within 1 day of stopping study medication, if possible. Such subjects should also complete the requisite 2-week follow-up period (see [Section 9.4.8](#)).

At the Week 16 visit, the following activities/procedures will be performed:

- Vital signs (heart rate and blood pressure should be assessed in a seated position after 5 minutes of rest and prior to blood draws)
- AE review (see [Section 10.3.6](#) for follow-up of unresolved events)
- Rescue therapy (ESA rescue and RBC transfusion) review
- Concomitant medication review
- Laboratory procedures:
  - Serum pregnancy test for females of childbearing potential (to be analyzed by the central lab)
  - CBC
  - Chemistry and eGFR
  - Iron indices
  - Hepcidin
  - C-reactive protein
  - VEGF
- Subjects should be questioned regarding dosing compliance

#### **9.4.8 Week 18 Follow-Up Visit (or 2 weeks after end-of-treatment follow-up visit)**

For subjects who complete the dose adjustment and maintenance period, the follow-up visit will be conducted 2 weeks after their end-of-treatment visit (Week 16).

For subjects who discontinue the study prematurely (ie, prior to Week 16), the follow-up visit will be conducted 2 weeks after their end-of-treatment visit.

At the follow-up visit, the following activities/procedures will be performed:

- Vital signs (heart rate and blood pressure should be assessed in a seated position after 5 minutes of rest and prior to blood draws)
- AE review (see [Section 10.3.6](#) for follow-up of unresolved events)
- Rescue therapy (ESA rescue and RBC transfusion) review
- Concomitant medication review
- Laboratory procedures:
  - CBC
  - Chemistry and eGFR

## 10 ADVERSE EVENTS

### 10.1 Definitions

#### 10.1.1 Adverse Events (AEs)

For the purposes of this study, an AE is any untoward medical occurrence (including a clinically significant abnormal laboratory finding) that occurs in the protocol-specified AE reporting period; the event does not necessarily have a causal relationship with that treatment or usage.

An AE includes medical conditions, signs, and symptoms not previously observed in the subject that emerge during the protocol-specified AE reporting period, including signs or symptoms associated with pre-existing underlying conditions that were not present prior to the AE reporting period.

Adverse events therefore include the following:

- All AEs, whether suspected to be causally related to study drug or otherwise.
- All AEs secondary to any medication overdose, medication error, abuse, withdrawal, sensitivity, or toxicity.
- Illnesses apparently unrelated to study drug, including the worsening of a pre-existing illness (see paragraph below on Pre-existing Conditions).
- Injury or accidents. Note that if a medical condition is known to have caused the injury or accident (eg, a fall secondary to dizziness), the medical condition (dizziness) and the accident (fall) should be reported as 2 separate AEs.
- Abnormalities in physiological testing or physical examination findings that require clinical intervention or further investigation (beyond ordering a repeat [confirmatory] test).
- Laboratory abnormalities that require clinical intervention or further investigation (beyond ordering a repeat [confirmatory] test) unless they are associated with an already reported clinical event. Laboratory abnormalities associated with a clinical event reported as an AE (eg, elevated liver enzymes in a subject with jaundice) should be described under ‘Comments’ on the report of the clinical event rather than reported as separate AEs.

The following guidelines are to be used when reporting AEs for this study:

**Medical Diagnoses** – Whenever possible, a medical diagnosis term should be used to report AEs instead of signs and symptoms due to a common etiology, as determined by qualified medical study staff. For example, pneumonia should be the reported AE term, instead of fever, dyspnea, etc., when the diagnosis has been established. Signs and symptoms should be reported as event terms only when the medical diagnosis remains unknown, and revised to a medical diagnosis term once it has been established.

**Procedures** – Diagnostic and therapeutic non-invasive and invasive procedures, such as surgery, should not be reported as AEs. However, the medical condition for which the procedure was performed should be reported if it meets the definition of an AE. For example, an acute appendicitis that begins during the AE reporting period should be reported as the AE and the resulting appendectomy noted under “Comments.”

Pre-planned therapeutic procedures not associated with a new medical condition or worsening pre-existing condition should not be reported as AEs.

**Pre-existing Conditions** – In this study, a pre-existing condition (ie, a disorder present before the AE reporting period started and noted on the pre-treatment medical history/physical examination form) should not be reported as an AE unless the condition worsens or episodes increase in frequency during the AE reporting period.

**Abnormal Test Findings** – All laboratory test results will be reviewed by the investigator. The investigator will utilize his/her judgment in determining if out of range laboratory values are clinically significant and should denote this using the abbreviation “CS” on the laboratory report for source documentation. Laboratory tests that are labeled as clinically significant should be reported as AEs, either separately or as part of a description of a symptomatic AE. If there are significant changes in a laboratory report from a previous visit that are determined to be clinically significant, these should also be reported as AEs. Any abnormal laboratory value which requires treatment or further diagnostic testing and/or results in discontinuation from study should be reported as AEs. An expected laboratory abnormality from a condition that is part of the medical history is not considered clinically significant for the purposes of the study unless it represents a worsening of the condition.

**Abnormalities in ALT, AST and Total Bilirubin** – Abnormalities in ALT, AST and total bilirubin should be reported to the sponsor’s medical monitor/medical director or CRO designee within 24 hours of awareness as an SAE with ‘other medically important event’ criterion selected, if the following conditions are met:

- New elevation in ALT or AST > 3 times the upper limit of normal (ULN), with or without an elevation of total serum bilirubin > 2 times ULN, AND
- No other reason was identified that explains the increased ALT/AST with or without an increased bilirubin (eg, viral hepatitis, acute liver disease).

If new elevations in ALT or AST > 3 times ULN, with or without an elevation of total serum bilirubin > 2 times ULN are identified, the following steps are to be taken:

- Temporary discontinuation of study medication.
- Repeat testing of ALT, AST, ALP and total bilirubin, to be completed within 48 to 72 hours to confirm the abnormalities and to determine trend.
- Study medication should not be resumed until monitoring indicates abnormalities have resolved, are stable, or are not rapidly increasing.

**Worsening of Anemia** – In this study, it is possible that some subjects may experience a worsening of anemia. Worsening of anemia should not be considered an AE unless the worsening of anemia is associated with a cause other than the subject’s CKD.

**Renal-Related Events** – Some subjects will experience a progression of their CKD during the study as part of the natural course of the disease. In addition, the study population is prone to experience acute, transient loss of kidney function of different etiologies, sometimes concomitantly complicated by progression of CKD.

To ensure consistent reporting of renal events, the following guidelines are to be used when reporting a renal-related AE:

- The following situations **should always be reported as SAEs** with the respective seriousness criteria selected (see [Section 10.1.2](#)):
  - **Progression of CKD leading to chronic dialysis**: Subjects who undergo transition to chronic maintenance dialysis should be reported using the verbatim SAE term of “progression to end-stage renal disease” (ESRD) and the additional seriousness criterion “chronic dialysis”
  - **Any medical event requiring transient acute dialysis**: Subjects who undergo transient acute dialysis should be reported using the verbatim SAE term reflecting the indication for the dialysis. Examples of verbatim AE terms include hyperkalemia, volume overload, acute kidney injury, and uremia. The additional seriousness criterion “acute dialysis” should be selected.
  - **Kidney transplantation**: Subject receiving a kidney transplant should be reported using the verbatim SAE term “Progression to ESRD”, with the additional serious criterion of “kidney transplant” selected.
- The following situations will be **reported as SAEs if they meet seriousness criteria** (see [Section 10.1.2](#)); otherwise, they should be reported as AEs:
  - **Acute kidney injury not requiring dialysis** – The reported AE term should reflect the etiology for the impairment of the renal function. Non-specific AE terms such as “Decreased eGFR” or “Increased creatinine” should be avoided whenever the underlying etiology is known.
    - Examples of verbatim AE terms for prerenal impairment include hypovolemia, hepatorenal syndrome, and heart failure
    - Examples of verbatim AE terms for intrarenal impairment include acute tubular necrosis, acute interstitial nephritis, and glomerulonephritis
    - Examples of verbatim AE terms for postrenal impairment include hydronephrosis, pelvicaliectasis, and urinary tract obstruction
  - **Progression of CKD not requiring dialysis** – If permanent loss of renal function due to underlying CKD has occurred, the reported AE term should reflect the underlying etiology. Non-specific terms such as “Decreased eGFR,” “Increased creatinine,” or “Worsening CKD” should be avoided whenever the underlying etiology is known. Examples of verbatim AE terms include worsening lupus nephritis, worsening diabetic kidney disease, and worsening glomerulonephritis.
  - **Medical conditions related to CKD that occur without acute kidney injury or progression of CKD** – If there is no decline in kidney function, the medical complication of CKD itself should be reported. AE terms such as “Progression of CKD” or “Acute Kidney Injury,” should be avoided when there is no decline in kidney function. Examples of AE terms include edema and hyperkalemia.

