## 7.3 Exclusion Criteria

Subjects who meet any of the following exclusion criteria will not qualify for study participation:

1. Anemia due to a cause other than CKD or presence of active bleeding or recent blood loss
2. Sickle cell disease, myelodysplastic syndromes, bone marrow fibrosis, hematologic malignancy, myeloma, hemolytic anemia, thalassemia, or pure red cell aplasia
3. RBC transfusion within 4 weeks prior to or during screening
4. Intravenous iron within 4 weeks prior to or during screening

5. Any ESA use within 6 weeks prior to or during screening (eg, recombinant human erythropoietin, darbepoetin alfa, or methoxy polyethylene glycol-epoetin beta)
6. Aspartate aminotransferase (AST)/serum glutamic oxaloacetic transaminase (SGOT), alanine aminotransferase (ALT)/serum glutamic pyruvic transaminase (SGPT), or total bilirubin  $>2.0 \times$  upper limit of normal during screening. A history of Gilbert's syndrome is not an exclusion criterion.
7. Uncontrolled hypertension (confirmed diastolic blood pressure  $>110$  mm Hg or systolic blood pressure  $>180$  mm Hg) during screening
8. Body mass index (BMI)  $>42.0 \text{ kg/m}^2$
9. Severe heart failure during screening (New York Heart Association Class III or IV)
10. History of untreated proliferative diabetic retinopathy, diabetic macular edema, age-related macular degeneration, central retinal vein occlusion, active retinal hemorrhage, or ongoing ocular treatment with laser photocoagulation or anti-VEGF therapies
11. Acute coronary syndrome (hospitalization for unstable angina or myocardial infarction), surgical or percutaneous intervention for coronary, cerebrovascular, or peripheral artery disease (aortic or lower extremity), surgical or percutaneous valvular replacement or repair, sustained ventricular tachycardia, hospitalization for heart failure, or stroke within 12 weeks prior to or during screening
12. History of active malignancy within 2 years prior to or during screening, except for treated basal cell carcinoma of skin, curatively resected squamous cell carcinoma of skin, cervical carcinoma in situ, or resected benign colonic polyps
13. History of deep vein thrombosis (DVT) or pulmonary embolism (PE) requiring active treatment within 8 weeks prior to or during screening
14. History of hemosiderosis or hemochromatosis

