### **7.6.2 Conditions and Documentation of Individual Subject Study Drug Discontinuation**

Subjects will discontinue study medication for any of the following conditions:

- Completion of the protocol-defined dosing period (see [Appendix A](#))
- Worsening of anemia requiring ESA rescue or blood transfusion
- Unacceptable toxicity or drug intolerance
- Investigator discretion
- Subject withdrawal of consent
- Subject becomes pregnant
- Other reasons

The investigator must document the primary reason for discontinuation in the appropriate case report form (CRF).

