### **10.3.3 Reporting SAEs**

Any SAE, regardless of causal relationship, must be reported to the sponsor's medical monitor/medical director or CRO designee **within 24 hours** after the investigator becomes aware of the SAE. Compliance with this time requirement is essential so that the sponsor may comply with its regulatory obligations.

The initial SAE report should be completed as fully as possible but should contain, at a minimum:

- Subject number/ID, sex, and age/date of birth
- The date of report
- Name of the reporter
- Description of the event, including event term(s), seriousness criteria, and a clinical summary of the event
- Causality assessment

Information about all SAEs (either initial or follow-up information) should be collected and recorded in English on the SAE Report Form. The investigator must assess the relationship to each specific component of the study treatment. If the event meets serious criteria, SAE Report Form should be sent to the CRO via email or fax, or the investigator should call the CRO SAE hotline within 24 hours of being made aware of the SAE (reference the site manual for contact information).

The investigator must report follow-up information relating to an SAE to the sponsor's medical monitor/medical director or CRO designee within 24 hours of awareness by submitting a new SAE Report Form. The subject should be observed and monitored carefully until the condition resolves or stabilizes.

All deaths are to be thoroughly investigated and reported. Autopsy reports are to be obtained, if possible, and sent to the CRO via email or fax.

The sponsor and/or its designee are responsible for reporting SAEs to all applicable regulatory agencies and the central ethics committees within the required timeline.

The investigators are responsible for submitting required safety information to their local Institutional Review Board (IRB) or Independent Ethics Committee (IEC) per local regulations. This information includes but is not limited to, any safety alert letter received from the sponsor and any SAEs occurring at their investigative site.

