#### 10.3.6 Follow-Up of Unresolved Events

All AEs should be followed until they are resolved or the investigator assesses them as chronic or stable or the subject’s participation in the trial ends.

In addition, all SAEs and those non-serious events assessed by the investigator as related to the study medication should continue to be followed even after the subject's participation in the trial is over. Such events should be followed until they resolve or until the investigator assesses them as "chronic" or "stable." Resolution of such events is to be documented on the appropriate CRF.

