### 11.2 Primary Efficacy Analysis and Sample Size Determination

An analysis of covariance (ANCOVA) model will be used to compare change from pre-treatment in Hb between the 3 vadadustat dosing groups and the placebo group. The model will include treatment assignment (3 dosed groups and 1 placebo group) and pre-treatment Hb value as a covariate. A step-down procedure will be used to control the overall type I error rate for the multiple comparisons. Testing of the highest dose compared with placebo will be conducted first. If and only if this comparison is significant, then testing will proceed to comparison of the next lower dose and placebo, and so on. Therefore, no multiplicity adjustment will be needed for this analysis.

The target enrollment will be approximately 48 subjects for the study with 12 subjects enrolled in each of the 4 treatment groups.

The study is powered based on a comparison of the highest dose vadadustat group (600 mg daily) and the placebo group. Based on the results from Study AKB-6548-CI-0005 that was conducted in the United States and evaluated vadadustat in patients with anemia secondary to

NDD-CKD, it is assumed that the expected mean Hb changes from baseline to Week 6 will be approximately 0 mg/dL for the placebo group and 1.35 g/dL for the highest dose vadadustat group (600 mg daily), with a common standard deviation of 0.68 g/dL across treatment groups. With these assumptions, the study with n=12 subjects per group will have >95% power to detect the difference between treatment group and control group, at 2-sided alpha of 0.05.

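### The liver restart condition permits, without requiring, re-dosing after an unexplained combined ALT/AST and bilirubin rise while both are still elevated, and after an unexplained isolated rise that has only levelled off above the 3x ULN hold level

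*Protocol*

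**What the plan says.** Protocol section 10.1.1, under abnormalities in ALT, AST and total bilirubin, attaches three steps to one trigger: "new elevations in ALT or AST > 3 times ULN, with or without an elevation of total serum bilirubin > 2 times ULN". Study drug is temporarily stopped. ALT, AST, ALP and total bilirubin are repeated within 48 to 72 hours, to confirm the finding and show its direction. Then comes the restart line: "Study medication should not be resumed until monitoring indicates abnormalities have resolved, are stable, or are not rapidly increasing". The liver text is the same in all three protocol versions in the file.

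Several other provisions bear on such a subject:

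- **Reporting.** When no other cause is identified, section 10.1.1 requires the abnormality to be reported "within 24 hours of awareness as an SAE with" the medically important criterion.
- **Monitoring of SAEs** (10.3.3): "The subject should be observed and monitored carefully until the condition resolves or stabilizes".
- **Follow-up after the trial** (10.3.6): "all SAEs and those non-serious events assessed by the investigator as related to the study medication should continue to be followed".
- **Stopping reasons** (7.6.2): these include "Unacceptable toxicity or drug intolerance" and investigator discretion.
- **Scheduled chemistry** (9.3.2, Appendix A): a panel with ALT, AST, ALP and total bilirubin is drawn at Weeks 2, 4, 6, 8, 10, 12, 14, 16 and 18.
- **Entry** (7.3): ALT, AST or total bilirubin above 2.0x ULN excludes, with the note that a history of Gilbert's "syndrome is not an exclusion criterion".

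**The concern.** The hold has a number and the restart has none. Of the three restart alternatives only resolution implies a return towards normal, and it is not required. The other two, stability and absence of a rapid rise, are undefined and describe direction rather than level.

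The combined rise is named in the trigger but has no path of its own: the same restart line applies as for an isolated ALT or AST rise. A subject with both abnormalities still present, and no non-drug explanation, can be put back on the possible cause within the protocol. Planned enrolment is at about 25 sites (section 6.1), so the level at which this happens would depend on individual judgment. Everyone who continues past Week 6 takes vadadustat until Week 16 (section 8.2.5), so re-exposure could last for weeks.

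**Working it through.** **1. The restart line as a condition.** Hold if new ALT or AST > 3x ULN, at any bilirubin. Restart allowed if resolved OR stable OR not rapidly increasing. The values below are illustrative and are not from the protocol.

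| Value at hold, then on retest | Alternative met | Restart permitted? |
|---|---|---|
| ALT 5x, then 5x ULN | stable | yes, above 3x ULN |
| ALT 5.0x, then 5.3x ULN | arguably not rapidly increasing | yes, above 3x ULN |
| Either of the above, bilirubin steady at 2.5x ULN | same | yes, both still elevated |
| ALT 5x, then 10x ULN | none | no |

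**2. Does other text narrow it?** The 24-hour report is notification; nothing makes restart wait for the medical monitor's agreement. SAE monitoring runs until resolution or stabilization, and a plateau above 3x ULN satisfies that. Follow-up concerns observing the event. Section 7.6.2 allows stopping but gives no liver level. Two-weekly chemistry would detect a later rise, after dosing has resumed. None of these sets a restart level.

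**3. Comparison within the protocol.** For haemoglobin, sections 8.2.4 and 8.2.5 interrupt drug above 13.0 g/dL and resume at 12.5 g/dL or below with one tablet fewer, so both a hold level and a restart level are given. For the liver only the hold level is given. Entry is barred above 2.0x ULN, so restart is permitted at values that would have excluded the subject.

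**4. What a stricter rule could cost in power.** Inputs are from section 11.2: "approximately 0 mg/dL for the placebo group and 1.35 g/dL for the highest dose vadadustat" group, SD 0.68 g/dL, n = 12 per group, two-sided alpha 0.05. A two-sample t test is used as an approximation to the ANCOVA.

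- *No hold.* d = 1.35/0.68 = 1.985; power 0.996, consistent with the stated figure of more than 95%.
- *One of 12 held for 14 of 42 days*, assuming effect proportional to days dosed. Loss 1.35 × 14/42 = 0.45 g/dL in that subject; 0.45/12 = 0.0375 g/dL in the arm mean. Mean 1.3125; pooled SD 0.686; power 0.994.
- *One of 12 losing the whole effect.* 1.35/12 = 0.1125 g/dL; mean 1.2375. Arm variance 0.68² + (1/12)(11/12)(1.35²) = 0.602; pooled SD √[(0.602 + 0.4624)/2] = 0.729; power 0.978.

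These charge the entire hold to the new rule. Section 10.1.1 already requires a hold, so only the extra days count and each figure is an upper bound on the loss in its scenario.

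**5. Per-protocol membership.** Section 11.4.2 requires at least 80% compliance but gives no denominator. If a directed hold counts as non-compliance, the allowance is 0.20 × 42 = 8.4 days over 6 weeks, or 0.20 × 112 = 22.4 days over 16 weeks.

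**The case against.** The protocol does have a liver rule, and the rule does not contradict itself. It holds drug at a numeric threshold on ALT or AST alone, requires a prompt retest and sets a trend-based condition. A reader might infer that the protocol tells sites to restart while liver tests are abnormal. It does not: the line states what must be true before restart and leaves the investigator free to decline. Nor is bilirubin ignored. It is in the mandated retest, and on a natural reading a rapidly rising bilirubin also bars restart. What is missing is a stricter path for the combined rise.

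A reader might also infer that any restart above 3x ULN is wrong. The documents do not support that. The condition that no other cause is found belongs only to the SAE report; the hold applies to every new rise above 3x ULN, including explained ones such as viral hepatitis. A hold that broad gives some reason to leave restart to judgment once a cause is known. A blanket ceiling for isolated, explained rises is a debatable trade-off, so the point is confined to unexplained rises and the combined rise.

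The size of the risk cannot be judged from these pages. The protocol calls vadadustat generally well tolerated, and the Investigator's Brochure it refers to is not at hand. Two-weekly chemistry also limits how long a worsening after restart could go unseen. These arguments lower the weight of the point but do not supply a restart level.

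**Conclusion.** The point stands in this limited form. The restart condition permits re-dosing after a combined rise with both abnormalities still present and no confirmed non-drug cause, and after an unexplained isolated rise that has plateaued or is rising slowly above 3x ULN. It is an explicit safety rule in the current text, and neither redaction nor an omitted analysis plan explains it.

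Confidence in the wording is high; confidence in the consequence is lower, because no event rate is given and few of 48 subjects are likely to be affected. The case rests on what the rule allows, not on a count. The power figures show only that tightening is affordable; they say nothing about how unsafe the present rule is. They assume the protocol's effect and SD and, for the 14-day case, effect proportional to days dosed. The change should be made, but the gap does not threaten the primary analysis.

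**What to change.** In section 10.1.1, replace the restart line with three cases:

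- After a combined rise of ALT or AST above 3x ULN and total bilirubin above 2x ULN, study medication is permanently discontinued unless a non-drug cause is confirmed, allowing for baseline bilirubin in known Gilbert's syndrome.
- After an isolated ALT or AST rise above 3x ULN with no other cause identified, study medication may be resumed only when ALT and AST are at or below 2x ULN (the entry limit in section 7.3) or at the subject's baseline, and not rising.
- Where a non-drug cause is confirmed, restart is at the investigator's judgment once values are stable or falling, after discussion with the medical monitor.

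Add the combined rise without a confirmed non-drug cause to the stopping reasons in section 7.6.2.

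The cost is a wording change plus somewhat longer holds or lost doses in a few subjects. MITT membership is unaffected. Because MITT is analysed as randomized, extra days off drug can dilute the Week 6 haemoglobin change, within the bounds shown above. A long hold could cost per-protocol membership, so the compliance denominator, and whether a directed hold counts against it, should be stated at the same time.
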